**Table 1. Treatment Sequences**

	Period 1	Washout (4 days between PF-07321332 dosing)	Period 2
Sequence 1 (n=6)	Treatment A		Treatment B
Sequence 2 (n=6)	Treatment B		Treatment A

The total planned duration of participation, from the screening visit to the last Follow-up phone call, is approximately 10 weeks. Participants will be screened within 28 days prior to the first dose of investigational products and if all eligibility criteria are fulfilled, the participants will report to the CRU on Day -1 and will be required to stay in the CRU for 8 days and 7 nights.

Eligible participants will be admitted to the CRU at least 12 hours prior to the dosing of PF-07321332 on Day 1. On the evening of Day -1, participants will receive a single oral dose of ritonavir 100 mg (-12 hour relative to PF-07321332/ritonavir dosing). On the morning of Day 1 of each period, participants will receive a single dose of PF-07321332 300 mg/ritonavir 100 mg as per randomization schedule. Study interventions will be administered with approximately 240 mL of ambient temperature water. In fed periods (Sequence 2, Period 1 and Sequence 1, Period 2), following an overnight fast of at least 10 hours, participants should begin breakfast approximately 30 minutes prior to PF-07321332/ritonavir administration. A high-fat (approximately 50% of total caloric content of the meal), high-calorie (approximately 800 to 1000 calories) breakfast will be consumed over approximately a 20-minute interval with PF-07321332/ritonavir administered within approximately 10 minutes of completion of the meal. Ritonavir, 100 mg, will continue to be dosed at 12 hours post PF-07321332 dosing. Serial PK samples will be collected up to 48 hours post dose. Period 2 will begin on Study Day 4 (referred to as Period 2, Day -1).

Participants will be discharged from the CRU on Period 2, Day 3 following completion of all assessments.

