## **6. STUDY INTERVENTION(S) AND CONCOMITANT THERAPY**

Study intervention is defined as any investigational intervention(s), marketed product(s), placebo, medical device(s), or study procedure(s) intended to be administered to a study participant according to the study protocol.

For the purposes of this protocol, study intervention refers to PF-07321332 and ritonavir.

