### 6.1.1. Administration

Investigational products will be administered orally and according to the conditions described in the [SoA](#) section and Protocol Section [5.3.1 Meals and Dietary Restrictions](#).

For **fasted** period (Sequence 1, Period 1 and Sequence 2, Period 2):

- On Day -1, 12 hours prior to dosing of PF-07321332, participants will receive a 100 mg ritonavir tablet (as 1 × 100 mg) with approximately 240 mL ambient temperature water. On Day 1, following an overnight fast of at least 10 hours, the participants will receive 300 mg PF-07321332 (as 2 × 150 mg tablets) with 100 mg ritonavir (as 1 × 100 mg tablet) administered orally at approximately 08:00 hours (plus or minus 2 hours) without breakfast/standard meal on Day 1. 12 hours after dosing of PF-07321332, participants will receive a 100 mg ritonavir tablet (as 1 × 100 mg) with approximately 240 mL ambient temperature water.

For **fed** periods (Sequence 2, Period 1 and Sequence 1, Period 2):

- On Day -1, 12 hours prior to dosing of PF-07321332, participants will receive a 100 mg ritonavir tablet (as 1 × 100 mg) with approximately 240 mL ambient temperature water. On Day 1, following an overnight fast of at least 10 hours, participants will receive breakfast approximately 30 minutes prior to dosing which is to be completed within approximately 20 minutes as outlined in Section [5.3.1 \(Meals and Dietary Restrictions\)](#). The participants will then receive 300 mg PF-07321332 (as 2 × 150 mg tablets) with 100 mg ritonavir (as 1 × 100 mg tablet) administered orally at approximately 08:00 hours (plus or minus 2 hours). 12 hours after dosing of PF-07321332, participants will receive a 100 mg ritonavir tablet (as 1 × 100 mg) with approximately 240 mL ambient temperature water.

For **all** periods:

- PF-07321332 and ritonavir will be dosed simultaneously (within no more than 5 minutes of each other). Investigator site personnel will administer study intervention during each period with ambient temperature water to a total volume of approximately 240 mL. Participants will swallow all tablet formulations whole, and will not manipulate or chew the study intervention prior to swallowing.
- In order to standardize the conditions on PK sampling days, all participants will be required to refrain from lying down (except when required for BP, pulse rate, and ECG measurements), eating, and drinking beverages other than water during the first 4 hours after dosing.

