## 6.8. Concomitant Therapy

Participants will abstain from all concomitant treatments, except for the treatment of adverse events and hormonal contraceptives that meet the requirements of this study in participants who are WOCBP (see [Appendix 4](#)).

Use of prescription or nonprescription drugs and dietary and herbal supplements are prohibited within 7 days or 5 half-lives (whichever is longer) prior to the first dose of study intervention. Limited use of nonprescription medications that are not believed to affect participant safety or the overall results of the study may be permitted on a case-by-case basis following approval by the sponsor. Acetaminophen/paracetamol may be used at doses of  $\leq 1$  g/day.

As PF-07321332 and ritonavir are both primarily metabolized by CYP3A4, concomitant use of any medications or substances that are strong inducers of CYP3A4 are prohibited within 28 days prior to dosing of investigational product. Additionally, ritonavir and PF-07321332 are inhibitors of CYP3A4. Therefore, medications highly dependent on CYP3A4 for clearance and for which elevated plasma concentrations may be associated with serious and/or life-threatening events are not permitted during dosing of PF-07321332/ritonavir, through 4 days after the last dose of PF-07321332/ritonavir.

All concomitant treatments taken during the study must be recorded with indication, daily dose, and start and stop dates of administration. All participants will be questioned about concomitant treatment at each clinic visit.

Treatments taken within 28 days before the first dose of study intervention will be documented as a prior treatment. Treatments taken after the first dose of study intervention will be documented as concomitant treatments.

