2.2. Study Design

This is a Phase 1, open-label, single dose, randomized, 2-treatment, 2-sequence, 2-period crossover study to evaluate the effect of a high-fat meal on the relative bioavailability of PF-07321332 boosted with ritonavir following single dose oral administration of PF-07321332 in combination with ritonavir using 150 mg tablet formulation of PF-07321332 in healthy adult participants. The study will consist of 2 treatments: a single oral dose of 300 mg PF-07321332 (2 × 150 mg tablets) under fasted conditions and 3 doses of 100 mg ritonavir at -12 hour, 0 hour and 12 hour related to PF 07321332 dosing (Treatment A), and a single oral dose of 300 mg PF 07321332 (2 × 150 mg tablets) under fed conditions and 3 doses of 100 mg ritonavir at -12 hour, 0 hour and 12 hour related to PF-07321332 dosing (Treatment B).

*There will be a total of 2 treatment sequences shown in **Table 2** with the assigned Treatments A or B in each treatment period.*

Table 2. Treatment Sequences

	Period 1	Washout (4 days between PF-07321332 dosing)	Period 2
Sequence 1 (n=6)	Treatment A		Treatment B
Sequence 2 (n=6)	Treatment B		Treatment A

Each enrolled participant will participate in 2 study periods to receive 2 different treatments according to the sequence determined by randomization:

- *Treatment A: Single oral dose of 300 mg PF-07321332 (2 × 150 mg tablets) under fasted conditions and 3 doses of 100 mg ritonavir at -12 hour, 0 hour and 12 hour related to PF-07321332 dosing. (Reference)*
- *Treatment B: Single oral dose of 300 mg PF 07321332 (2 × 150 mg tablets) under fed conditions and 3 doses of 100 mg ritonavir at -12 hour, 0 hour and 12 hour related to PF-07321332 dosing. (Test)*

A total of approximately 12 healthy male and/or female participants will be randomly assigned to investigational product such that approximately 6 participants will be enrolled to each sequence. Participants who withdraw from the study may be replaced at the sponsor's discretion in collaboration with the Investigator.

The total planned duration of participation, from the screening visit to the last Follow-up phone call, is approximately 10 weeks. Participants will be screened within 28 days prior to the first dose of investigational products and if all eligibility criteria are fulfilled, the participants will report to the CRU on Day -1 and will be required to stay in the CRU for 8 days and 7 nights.

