3.5. Safety Endpoints

3.5.1. Adverse Events

An adverse event is considered a Treatment-Emergent Adverse Event (TEAE) if the event started during the effective duration of treatment. All events that start on or after the first dosing day and time/start time, if collected, but before the end of the study will be flagged as TEAEs. The algorithm will not consider any events that started prior to the first dose date of PF-07321332.

A 3-tier approach for summarizing AEs will not be used due to the low number of participants planned to be recruited.

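### The TEAE rule in SAP 3.5.1 leaves out events in the hours after the first study intervention dose, the ritonavir dose on the evening of Period 1 Day -1

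*SAP*

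**What the plan says.** SAP 3.5.1 defines treatment emergence in three steps.

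1. The general definition: "An adverse event is considered a Treatment-Emergent Adverse Event (TEAE) if the event started during the effective duration of treatment".
2. The operational rule, which flags "All events that start on or after the first dosing day and time/start time, if collected, but before the end of the study". It names no product.
3. The restriction: "The algorithm will not consider any events that started prior to the first dose date of PF-07321332".

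The surrounding text fixes when treatment begins.

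- Protocol 6: "For the purposes of this protocol, study intervention refers to PF-07321332 and ritonavir".
- Protocol 4.1, below Table 1: "On the evening of Day -1, participants will receive a single oral dose of ritonavir 100 mg". This is 12 hours before PF-07321332. Protocol 6.1.1 repeats the timing for fasted and fed periods and places the PF-07321332 dose at about 08:00, give or take 2 hours.
- SAP 2.2 describes each of the two treatments as including "3 doses of 100 mg ritonavir at -12 hour, 0 hour and 12 hour related to PF 07321332 dosing".
- SAP 4 admits to the Safety Analysis Set any randomized participant who took one dose of study intervention. The lead-in ritonavir dose alone is enough.
- SAP 2.1 lists TEAEs as a secondary endpoint, under an objective on the safety and tolerability of PF-07321332/ritonavir.

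**The concern.** The restriction starts the TEAE clock at the first dose date of one of the two study drugs, and the other drug is given first. An event on the evening of Period 1 Day -1, after the lead-in ritonavir dose, occurs in someone who is already in the Safety Analysis Set and has received part of the assigned treatment. The rule nevertheless classes it as not treatment-emergent. No other section of the protocol or SAP brings it back.

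At stake is the classification of a named secondary endpoint. The safety objective covers the combination, and Protocol 2.3.1 lists risks specific to ritonavir, including gastrointestinal and neurological disturbances. The hours left out follow each participant's first ritonavir dose in the study. The wording also leaves room for two programmers to produce different TEAE tables from the same data.

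**Working it through.** **Inputs.** PF-07321332 at 08:00 ± 2 h on Day 1 (Protocol 6.1.1). Ritonavir at -12, 0 and +12 h in each period (SAP 2.2). Period 2 Day -1 is Study Day 4 (Protocol 4.1). Follow-up contact 28 to 35 days after the last dose (Schedule of Activities, footnote w). About 12 participants, 6 per sequence. The plan gives no figure of its own to reproduce.

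**Clock times in Period 1.** Lead-in time = PF-07321332 time − 12 h.

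| PF-07321332, Day 1 | Ritonavir, Day -1 | Lead-in to midnight | Midnight to PF-07321332 |
|---|---|---|---|
| 06:00 | 18:00 | 6 h | 6 h |
| 08:00 | 20:00 | 4 h | 8 h |
| 10:00 | 22:00 | 2 h | 10 h |

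**Lead-in to midnight (2 to 6 h).** These events start before the first PF-07321332 dose date, so the third sentence excludes them. If the second sentence means the first ritonavir dose, it flags them and the third sentence then removes them. If it means PF-07321332, the two sentences agree with each other, but the TEAE window opens after treatment as SAP 2.2 describes it has begun.

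**Midnight to the PF-07321332 dose (6 to 10 h).** These events fall on the dose date, so the third sentence does not exclude them. Where start times are collected, they are TEAEs if the second sentence means ritonavir and are not if it means PF-07321332. The SAP does not say which.

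**Period 2.** Period 2 Day 1 is Study Day 5, which is 4 × 24 = 96 h after the first PF-07321332 dose. The Period 2 lead-in dose comes at 96 − 12 = 84 h, so events after it are not excluded. The restriction affects the hours after 1 of the 6 ritonavir doses per participant.

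**Size as a share of time.**
- First to last study intervention dose: 12 + 96 + 12 = 120 h.
- First dose to follow-up contact: 120 + 28 × 24 = 792 h, up to 120 + 35 × 24 = 960 h.
- Certainly excluded: 2/120 = 1.7% to 6/120 = 5.0% of the dosing interval; 2/960 = 0.2% to 6/792 = 0.8% of the time to follow-up.
- If the unclear hours are excluded too: 12/120 = 10% of the dosing interval; 12/960 = 1.3% to 12/792 = 1.5% of the time to follow-up.

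**Size in the tables.** With 12 participants per treatment, moving one event into the TEAE set changes that treatment's any-TEAE incidence by 1/12 = 8.3 percentage points if the participant has no other TEAE under it, and by 0 otherwise. Event counts, and the incidence of that particular event term, can change in either case.

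**The case against.** The PF-07321332 anchor may be deliberate. Laboratory, vital-sign and ECG baselines in SAP 3.5.2 to 3.5.4 are all set relative to the first PF-07321332 dose, and Protocol 2.2 describes ritonavir as a PK booster only. On the evening of Day -1 the two treatments are identical, so an event then carries no information about the meal. No hypothesis is tested (SAP 5.1), and the listed ritonavir risks come from a much higher dose, 600 mg twice daily. Also, the phrase in the first sentence about the effective duration of treatment is never defined, so the next two sentences could be read as its definition.

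Most of this bears on size, and there it stands: the effect is minor, and nothing suggests a distorted fed-versus-fasted comparison. It does not rescue the rule. A baseline definition says which measurement is the reference; it does not say when treatment starts. The SAP states no reason for excluding the lead-in hours, and counting the same hours in Period 2 sits badly with such a reason. The mismatch with the definition of study intervention, the Safety Analysis Set and the safety objective does not depend on the undefined phrase.

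A reader might also infer a clash with Protocol 6.8: "Treatments taken after the first dose of study intervention will be documented as concomitant treatments". A medicine given that evening for an adverse event would be concomitant while the event itself is not treatment-emergent. That looks untidy but is not a contradiction. One rule governs how medicines are documented, the other an adverse event flag, and nothing requires them to share a cut-off.

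**Conclusion.** The point holds as a small but definite error in a secondary endpoint definition. Per participant, 2 to 6 hours on study intervention are certainly outside the TEAE window, in Period 1 only, and another 6 to 10 hours are undetermined. The hours assume dosing within the protocol's clock window. The step of 1/12 assumes that all 12 participants receive both treatments.

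Stronger readings are tempting, but the documents do not support them.

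- *Safety data are lost.* They are not. Adverse events are collected from consent and recorded on the CRF (Protocol 8.3.1 and 8.3.1.2). Only the flag is affected.
- *A full 12 hours is excluded.* That follows only if the second sentence refers to PF-07321332, which it does not say.
- *A known number of events will be missed.* The documents give no event rate for these hours, so no count can be claimed.
- *All Period 1 baselines are taken after the lead-in dose.* This is so for ECG and vital signs, which are scheduled predose on Day 1. Period 1 safety laboratory tests are scheduled on Day -1.

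**What to change.** In SAP 3.5.1, use one anchor in both the second and third sentences: the date and time of the first dose of any study intervention, which is the Period 1 Day -1 ritonavir dose. Delete the restriction to the first PF-07321332 dose date. Suitable wording would be: *Events starting at or after the date and time of the first dose of any study intervention (ritonavir, Period 1 Day -1) and before the end of the study are flagged as TEAEs; events starting earlier are not.*

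Leave the baseline definitions in SAP 3.5.2 to 3.5.4 as they are. If a note is added, limit it to Period 1 ECG and vital signs.

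The cost is two edited sentences and a changed reference date-time in the adverse event program. Dose dates and times are already recorded on the CRF (Protocol 6.4), so no new data are needed. There are two downsides. The TEAE count may be slightly higher. And because the Period 1 ECG and vital-sign baselines follow the lead-in dose, an overnight finding could be both the baseline value and a TEAE; a note would make that visible but would not remove it.

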3.5.2. Laboratory Data

Safety laboratory tests will be performed as described in the protocol.

Baseline will be the last pre-dose measurement prior to administration of PF-07321332 in period 1.

To determine if there are any clinically significant laboratory abnormalities, the hematological, clinical chemistry (serum) and urinalysis safety tests will be assessed against the criteria specified in the sponsor reporting standards. The assessment will take into account whether each participant's baseline test result is within or outside the laboratory reference range for the particular laboratory parameter.

3.5.3. Vital Signs

Single supine blood pressure, respiratory rate, temperature and pulse measurements will be taken at times detailed in the SoA given in the protocol.

Baseline will be the last pre-dose measurement prior to administration of PF-07321332 in period 1.

The following vital signs endpoints will be determined:

- Change from baseline in supine systolic and diastolic blood pressure, pulse rate, temperature and respiratory rate.

3.5.4. ECG

12-lead ECGs will be recorded on all participants at times detailed in the SoA given in the protocol.

Baseline will be the last pre-dose measurement prior to administration of PF-07321332 in period 1.

The following ECG endpoints will be determined:

- Change from baseline in QT interval, heart rate, QTcF interval, PR interval, and QRS complex.

4. ANALYSIS SETS (POPULATIONS FOR ANALYSIS)

Data for all participants will be assessed to determine if participants meet the criteria for inclusion in each analysis population prior to unblinding and releasing the database and classifications will be documented per standard operating procedures.

Population	Description
Enrolled	“Enrolled” means a participant’s, agreement to participate in a clinical study following completion of the informed consent process and screening. Potential participants who are screened for the purpose of determining eligibility for the study, but do not participate in the study, are not considered enrolled, unless otherwise specified by the protocol. A participant will be considered enrolled if the informed consent is not withdrawn prior to participating in any study activity after screening.
Safety Analysis Set	All participants randomly assigned to study intervention and who take at least 1 dose of study intervention. Participants will be analyzed according to the product they actually received.
PK Concentration Set	All participants randomly assigned to study intervention and who take at least 1 dose of study intervention and in whom at least 1 concentration value is reported.
PK Parameter Set	All participants randomly assigned to study intervention and who take at least 1 dose of study intervention and in whom at least 1 of the PK parameters of interest are reported.

5. GENERAL METHODOLOGY AND CONVENTIONS

5.1. Hypotheses and Decision Rules

There is no statistical hypothesis testing planned for this study and no statistical decision rules will be applied.

5.2. General Methods

Unless otherwise stated, all summaries and plots will be presented by treatment.

5.2.1. Analyses for Continuous Endpoints

Continuous variables will be presented using summary statistics: number of observations, arithmetic mean, standard deviation, cv%, median, minimum and maximum values.

Log transformed continuous variables will be presented using summary statistics: number of observations, arithmetic mean, median, cv%, standard deviation, minimum, maximum, geometric mean and geometric cv%.

5.2.2. Analyses for Categorical Endpoints

Categorical variables will be presented using summary statistics: number of observations and percentages.

5.3. Methods to Manage Missing Data

For the analysis of safety endpoints, the sponsor data standard rules for imputation will be applied.

In all PK concentration data presentations (except listings), concentrations below the limit of quantification (BLQ) will be set to zero.

In listings, BLQ values will be reported as “<LLQ”, where LLQ will be replaced with the value for the lower limit of quantification (LLQ).

For PK summary tables and plots of mean/median profiles, statistics will be calculated having set concentrations to missing if 1 of the following cases is true:

1. A concentration has been collected as ND (ie not done) or NS (ie no sample),
2. A deviation in sampling time is of sufficient concern or a concentration has been flagged anomalous by the pharmacokineticist/statistician.

If a PK parameter cannot be derived from a participant's concentration data, the parameter will be coded as NC (ie not calculated). (Note that NC values will not be generated beyond the day that a participant discontinues). In summary tables, statistics will be calculated by setting NC values to missing; and statistics will be presented for a particular dose with ≥ 3 evaluable measurements. For statistical analyses, PK parameters coded as NC will also be set to missing; and analyses will not be performed for a particular parameter if more than 50% of the data are NC.

If an individual participant has a known biased estimate of a PK parameter (due for example to an unexpected event such as vomiting before all the compound is adequately absorbed in the body), this will be footnoted in summary tables and will not be included in the calculation of summary statistics or statistical analyses.

6. ANALYSES AND SUMMARIES

For all outputs produced, the following treatment labels and ordering will be used:

PF-07321332 300 mg/ritonavir 100 mg Fed

PF-07321332 300 mg/ritonavir 100 mg Fasted

6.1. Primary Endpoint(s)

The plasma PK parameters detailed in Section 3.3 will be listed and summarized for participants in the PK Parameter Set (as defined in Section 4). Missing values will be handled as detailed in Section 5.3. Each PK parameter will be summarized by treatment. Each summary will include the set of summary statistics as specified in Table 4.

Table 4. PK Parameters to be Summarized Descriptively

Parameter	Summary Statistics
AUC _{last} , AUC _{inf} , C _{max} , CL/F and V _z /F	N, arithmetic mean, median, cv%, standard deviation, minimum, maximum, geometric mean and geometric cv%.
T _{max}	N, median, minimum, maximum.
t _{1/2}	N, arithmetic mean, median, standard deviation, minimum, maximum.

For AUC_{inf}, AUC_{last} and C_{max} a listing of the individual participant ratios (Treatment B (fed)/Treatment A (fasted)) will be provided. Box and whisker plots for individual participant parameters (AUC_{inf}, AUC_{last} and C_{max}) will be presented by treatment and overlaid with geometric means.

Supporting data from the estimation of t_{1/2} will be listed by treatment where applicable: terminal phase rate constant (k_{el}); goodness of fit statistic from the log-linear regression (r²); the percent of AUC_{inf} based on extrapolation (AUC_{extrap%}); and the first, last, and number of time points used in the estimation of k_{el}. These data may be included in the CSR.

Presentations for PF-07321332 concentrations will be presented using participants in the PK Concentration Set (as defined in Section 4) and will include:

- a listing of all concentrations sorted by participant ID, treatment and nominal time post-dose. The concentration listing will also include the actual times. Deviations from the nominal time will be given in a separate listing.
- a summary of concentrations by treatment and nominal time post-dose, where the set of statistics will include n, mean, median, standard deviation, coefficient of variation (cv), minimum, maximum and the number of concentrations above the lower limit of quantification.
- individual concentration-time plots by treatment (on both linear and semi-log scales) against actual time post-dose (there will be separate spaghetti plots for each treatment per scale).
- individual concentration-time plots by participant (on both linear and semi-log scales) against actual time post-dose (there will be separate spaghetti plots for each participant per scale).

- median concentration-time plots (on both linear and semi-log scales) against nominal time post-dose by treatment (both treatments on the same plot per scale, based on the summary of concentrations by treatment and time post-dose).
- mean concentration-time plots (on both linear and semi-log scales) against nominal time post-dose by treatment (both treatments on the same plot per scale, based on the summary of concentrations by treatment and time post-dose).

The scale used for the x-axis (time) of these plots will be decided on review of the data, and will depend on how long PF-07321332 concentration is quantifiable in the matrix.

For summary statistics, median and mean plots by sampling time, the nominal PK sampling time will be used. For individual participant plots by time, the actual PK sampling time will be used.

Natural log transformed AUC_{inf} (if data permit), AUC_{last} and C_{max} will be analyzed using a mixed effect model with sequence, period and treatment as fixed effects and participant within sequence as a random effect. The Kenward-Roger adjustment for the degrees of freedom will be used. Estimates of the adjusted mean differences (Test-Reference) and corresponding 90% CIs will be obtained from the model. The adjusted mean differences and 90% CIs for the differences will be exponentiated to provide estimates of the ratio of adjusted geometric means (Test/Reference) and 90% CI for the ratios. Treatment A (PF-07321332/ritonavir administered under fasted condition) is the Reference treatment and Treatment B (PF-07321332/ritonavir administered under fed condition) is the Test treatment.

